If a new lesion is equivocal, for example because of its small size, continued therapy and follow-up evaluation will clarify if it represents truly new disease. If repeat scans confirm there is definitely a new lesion, progression should be declared using the date of the initial scan.

Criteria for Overall Response at a Single Time point

Table 21 provides a summary of the overall response status calculation at each response assessment time point for patients who have measurable disease at baseline.

Table 21: Criteria for Overall Response at a Single Time Point: Patients with Target Lesions (with or without Nontarget Lesions)

Target Lesions	Nontarget Lesions	New Lesions	Overall Response
CR	CR	No	CR
CR	Non-CR/non-PD	No	PR
CR	Not all evaluated	No	PR
PR	Non-PD or not all evaluated	No	PR
SD	Non-PD or not all evaluated	No	SD
Not all evaluated	Non-PD	No	NE
PD	Any	Yes or no	PD
Any	PD	Yes or no	PD
Any	Any	Yes	PD

Abbreviations: CR = complete response; NE = not evaluable; PD = progressive disease; PR = partial response; SD = stable disease

Missing Assessments and Not-Evaluable Designation

When no imaging/measurement is done at all at a particular time point, the patient is not evaluable at that time point. If measurements are made on only a subset of target lesions at a time point, usually the case is also considered not evaluable at that time point, unless a convincing argument can be made that the contribution of the individual missing lesions would not change the assigned time point response. This would be most likely to happen in the case of PD. For example, if a patient had a baseline sum of 50 mm with three measured lesions and during the study only two lesions were assessed, but those gave a sum of 80 mm, the patient will have achieved PD status, regardless of the contribution of the missing lesion.

Special Notes on Response Assessment

Patients with a global deterioration in health status requiring discontinuation of treatment without objective evidence of disease progression at that time should be reported as “symptomatic deterioration.” Every effort should be made to document objective progression even after discontinuation of treatment. Symptomatic deterioration is not a descriptor of an objective response; it is a reason for stopping study therapy. The objective response status of such patients is to be determined by evaluation of target and nontarget lesions as shown in [Table 21](#).

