For records with a missing procedure date, the following procedure will be employed for use in determining whether the procedure is prior or concomitant:

- Procedure dates with a missing day and non-missing month will be assumed to occur on the first day of the non-missing month, except for

- procedures occurring in the month of first dosing, in which case the date will be the date of first dosing.
- Procedure dates with missing day and month will be assumed to occur on the first day of the non-missing year (i.e., January 1), except for procedures occurring in the year of first dosing, in which case the date will be the date of first dosing.

For records with a missing disease progression date from prior therapy, the following procedure will be employed for use in analyzing time to event endpoints:

- If the disease progression date is completely missing OR only the year is available, set as missing.
- If both year and month of disease progression date from are available and only day is missing, the date of disease progression will be imputed by the last day of the month.

For records with a partial death date, the following procedure will be employed for use in deriving time to event variables.

- The death date will be imputed by the earliest possible date that is not contradicting with any other available data in the database.

All other data will be reported as they are collected. No imputation methods will be used to replace missing data unless otherwise stated in this document.

D. Interim Analyses

This is a single-arm, open-label study, so interim analyses may be performed as the study progresses.

Details of analysis will follow each section described in this SAP, may including the following components:

- Disposition
- Protocol deviations
- Baseline characteristics: demographics, disease history, medical history, concomitant medication/procedure
- Key components from efficacy analysis
- Key components from safety analysis
- PK and pharmacodynamic data (as available)

E. Analysis Populations

1. Safety Population

The safety population includes participants who were enrolled, allocated to treatment, and received at least one dose of investigational product.

2. Efficacy Population

The efficacy population includes participants who received study drug and had an on-treatment response assessment (including “Not Evaluable”) or who discontinued study before any response assessment performed due to disease progression.

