Patients receiving different dosing schedules will be presented in the listings only. Figures will be produced when specified.

Dates in the clinical database are classified into the categories of procedure dates, log dates, milestone dates, outcome dates, and special dates.

- Procedure Dates are the dates on which given protocol-specified procedure are performed. They include the dates of laboratory testing, physical examinations, tumor scans, etc. They should be present whenever data for a protocol-specified procedure is present and should only be missing when a procedure is marked as NOT DONE in the database. Procedure dates will not be imputed.
- Log Dates are dates recorded in CRF data logs. Specifically, they are the start and end dates for adverse events and concomitant medications/procedures. They should not be missing unless an event or medication is marked as ongoing in the database. Otherwise, incomplete log dates will be imputed according to the rules in Section 5.3. However, in listings, log dates will be shown as recorded without imputation.
- Milestone Dates are dates of protocol milestones such as randomization, study drug start date, study drug termination date, study closure date, etc. They should not be missing if the milestone occurs for a subject. They will not be imputed.
- Outcome Dates are dates corresponding to study endpoints such as survival, progression, etc. In most cases they are derived either from a milestone (e.g., the survival date is derived from the death date), or a procedure date (e.g., the progression date is derived from the date of the tumor scan that was used to determine progression). They may be subject to endpoint-specific censoring rules if the outcome did not occur but are not otherwise subject to imputation.
- Special Dates cannot be classified in any of the above categories and they include the date of birth. They may be subject to variable-specific censoring and imputation rules.

Calculations using dates (e.g., subject's age or relative day after the first dose of study medication) will adhere to the following conventions:

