screening, then end of even-numbered cycles, cycle 2, 4 and additional cycles, and within 14 days after last dose at end of treatment/early termination visit.

- RECIST v1.1 will be used to determine response for patients with solid tumors. The response categories of target lesions include complete response (CR), partial response (PR), stable disease (SD), progressive disease (PD), and not evaluable (NE). The response categories of non-target lesions include: CR, Non-CR/Non-PD, and PD. The appearance of new malignant lesions denotes disease progression. An overall response will be summarized taking all target lesion, non-target lesion, new lesion into consideration.
- iRECIST is an extension of RECIST 1.1 that allows for assessment of response in patients being treated with immunotherapeutic agents. Overall response per iRECIST will be captured in the eCRF. According to iRECIST (protocol appendix 2), target lesions, non-target lesion and new lesion will be continually measured per RECIST response criteria after disease progression. For patients who are assessed as PD by RECIST (Target or Non-target lesions), they will perform repeated response assessments by RECIST and the response will be collected according to the eCRF. If the repeated assessments show PD again, the patients are confirmed as PD in the first assessment. If the repeated assessments show CR, PR or SD, the patients are not confirmed as PD. The appearance of any new lesions is considered as disease progression per RECIST 1.1.
- LYRIC evaluates response in patients with lymphoma who are being treated with immunotherapeutic agents. The response of lymphoma will be assessed separately for CT-based assessment and PET-CT based assessment. CT-based assessment includes complete radiologic response, partial remission, stable disease, progressive disease, immune response 1, immune response 2, immune response 3 and not evaluable. PET-CT based assessment includes complete metabolic response, partial metabolic response, no metabolic response, progressive metabolic disease, immune metabolic response 1, immune metabolic response 2, immune metabolic response 3 and not evaluable. Combined Overall Response includes complete response (CR), partial response (PR), stable disease (SD), progressive disease (PD), immune response 1 (IR1), immune response 2 (IR2), immune response 3 (IR3), and not evaluable (NE).

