- If the repeated assessment confirmed as no disease progression and later SD, PR or CR occur, the initial diagnosis of PD will not be considered as the endpoint. Patients will continue further assessments until consecutive disease progression assessments occur.
- If the repeated assessment confirmed no disease progression and no later SD, PR or CR occur, and patients stop treatment due to not clinically stable or the patients die from their cancer, then the first unconfirmed progression should still be used as the endpoint (Seymour et al 2017).
- If the patients do not do a repeat assessment due to any other reasons, the unconfirmed PD date will be used as the endpoint.

For patients with lymphoma and evaluated by LYRIC, if they are categorized as having any of the IR response, repeat imaging should be obtained after an additional 12 weeks.

- If a patient is assessed as having IR and then “true” progressive disease at a subsequent time point, the IR assessment should subsequently be corrected to progressive disease and the date will be used as the PD endpoint for the relevant time to event analysis,
- If repeated imaging could not be obtained, the IR category will still be used as the endpoint.
- **Time to Progression (TTP):** defined as the time from the first SYNB1891 injection (Day 1) to PD. Patients who complete the study without PD or death will be censored at the day of their last visit. Patients

who discontinue or die due to disease progression, the endpoint will be the last assessment date prior to discontinue or death. Patients who discontinue or die not due to disease progression will be censored at their last tumor assessment.

- **Progression Free Survival (PFS):** defined as the time from the first SYNB1891 injection (Day 1) to PD or death, whichever is first, from any cause. Patients who complete or discontinue the study without disease progression or death will be censored at the last Response assessment date.

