- **Duration of Response:** defined as the time from the first day the patient achieves objective response (PR or CR) to the day the patient's response falls to PD. Patients who do not achieve an objective response of a PR or CR during the study are excluded from this analysis. Patients who achieve objective response and remain the response at the end of the study will be censored at their last tumor assessment visit. If patients discontinued study due to disease progression after achieving objective response, they will not be censored, and disease progression date will be the endpoint. If patients discontinued study not due to disease progression after achieving objective response, they will be censored at their last tumor response assessment date.

Waterfall plots for tumor response by individual will be presented. The plots will have one bar per subject sorted from worst to best response with color by dose administered. Tumor response will be calculated based on the type of cancer that the patient has with the appropriate measure using either RECIST or LYRIC; an indicator will be placed on the figure to show if the response for each subject is from “R”, RECIST, or “L”, LYRIC. One waterfall plot will indicate best tumor response (minimum percent change from baseline) at any time point for each subject. One waterfall plot will represent injected and non-injected tumors.

Spaghetti plots for tumor response by time will be presented. One line will be drawn per subject with color by response type (see Section VII.2). The horizontal axis will be time and the vertical axis will be percent change from baseline in tumor response. One spaghetti plot will be generated for all patients at all times. One set of spaghetti plots will be generated with one panel per analysis type (RECIST/ iRECIST, or LYRIC) and only patients who apply for the current analysis type will be shown.

Swimmer plots will be generated with panels by analysis type (RECIST/iRECIST, or LYRIC). The plots will have one horizontal bar per subject firstly sorted by best response type (see Section VII.2), and then sorted by from best to worst time to start that response; when best to worst time to start that response does not apply (e.g. NE for RECIST), patients will be sorted by

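### PFS, DOR and TTP censoring dates are not limited to evaluable tumor assessments, so a trailing Not Evaluable scan (or, for TTP, any last visit) extends event-free time

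*SAP*

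**What the plan says.** SAP VII.A.3 (Determination of Time to Event Endpoints) uses several different censoring dates and defines none of them.

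- **PFS:** "Patients who complete or discontinue the study without disease progression or death will be censored at the last Response assessment date".
- **DOR, response ongoing at the end of the study:** such patients "will be censored at their last tumor assessment visit".
- **DOR, discontinued for a reason other than progression:** "they will be censored at their last tumor response assessment date".
- **TTP, completers without progression or death:** the day of the last visit of any kind. Patients who leave or die for reasons other than progression are censored at the last tumor assessment.

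No rule there mentions NE. Elsewhere NE is treated as a response assessment or a response category:

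- The Efficacy Population (SAP V.E.2), on which these analyses run, admits treated patients who "had an on-treatment response assessment (including “Not Evaluable" (the parenthesis closes there).
- SAP VII.A.1 ends its list of RECIST target-lesion categories with "progressive disease (PD), and not evaluable (NE"), and NE is also a LYRIC combined overall response.
- SAP VII.A.2 places NE last in the RECIST best-response order and keeps NE patients in the response-rate denominators.

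Two further texts bear on missed scans. Protocol Appendix 1 says: "When no imaging/measurement is done at all at a particular time point, the patient is not evaluable at that time point". SAP V.F treats a tumor scan date as a procedure date, which "should only be missing when a procedure is marked as NOT DONE in the database. Procedure dates will not be imputed".

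**The concern.** Without an event, progression status is known only up to the last scan that allowed it to be judged. A censoring date later than that keeps the patient in the risk set, event-free, across an interval with incomplete information. Because the censoring section does not exclude NE and other sections count it, a programmer following the SAP's own usage would censor at a dated NE. No rule sends a patient whose only assessment is NE back to Day 1.

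Dated NE scans can occur. Under Protocol Appendix 1, measuring only some of the target lesions usually gives NE. A patient who can no longer have contrast, and for whom no substitute imaging works, is not evaluable from then on, so NEs can accumulate.

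At stake are the Kaplan-Meier medians, quartiles and PFS graphs by arm and cohort (SAP VII.A.3). Two programmers could also produce different curves from the same data.

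**Working it through.** The plan gives no PFS or DOR figure to reproduce. The check compares two rules: **A**, censor at the last dated assessment including NE; **B**, censor at the last evaluable assessment, or Day 1 if there is none.

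**Inputs from the documents.** Cycles last 21 days (SAP III.A) and imaging is every 2 cycles (SAP IV.B), so the interval is 2 × 21 = 42 days. Each dose level enrolls 3 to 14 patients (Protocol 4.2.3).

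**Direction.** The events are the same under A and B. Every censoring time under A is at least as late, so every risk set is at least as large. Each factor (1 − d/n) is therefore at least as large, and the PFS curve under A is never below the curve under B.

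**Per patient.**

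- SD at day 42, NE at day 84, then off study: A gives 84 days, B gives 42, a difference of 42.
- Two trailing NEs: 2 × 42 = 84 extra days.
- Only assessment is NE at day 42: A gives 42 days, B gives Day 1.

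**A cohort of three (illustration).** One PD at day 42, one PD at day 84, and the SD/NE patient above.

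- Rule A: S(42) = 1 − 1/3 = 0.667; S(84) = 0.667 × (1 − 1/2) = 0.333. The 75th percentile is not reached.
- Rule B: S(42) = 0.667; S(84) = 0.667 × (1 − 1/1) = 0. The 75th percentile is day 84.
- The median is day 84 under both rules.

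**Simulation, 40,000 patients per scenario.** None of these inputs comes from the documents: exponential progression with median 60, 90 or 120 days; exponential dropout without progression, mean 90 or 180 days; each scan independently NE with probability 5%, 10% or 20%; every NE dated; no separate deaths. Ranges are over the three medians.

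| Mean dropout | NE per scan | Patients affected | Day-126 PFS, A minus B (points) |
|---|---|---|---|
| 180 days | 5% | 1.6–2.2% | 0.4–0.5 |
| 180 days | 10% | 3.3–4.4% | 0.9–1.0 |
| 180 days | 20% | 6.9–9.0% | 2.0–2.3 |
| 90 days | 5% | 1.9–2.3% | 0.8–0.9 |
| 90 days | 10% | 3.9–4.7% | 1.7–1.8 |
| 90 days | 20% | 7.7–9.3% | 3.5–3.9 |

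Affected patients gain 42 to 50 days on average. The Kaplan-Meier median is the same under A and B in 15 of 18 scenarios. In the other three, all with a true median of 120 days, it is 168 days under A and 126 under B.

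**TTP for completers (nominal days, last dose at Cycle 35).** The Cycle 34 scan falls on day 34 × 21 = 714 and the last dose on day 715. The end-of-treatment visit falls by day 715 + 14 = 729, only 15 days after that scan, so the 8-week exception allows no new scan. Safety follow-up, with no imaging in the schedule, falls on day 715 + 30 ± 5 = 740 to 750. Censoring at the last visit then credits 26 to 36 days beyond the last scan.

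**The case against.** Much of the opposing case stands, and it limits the point.

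**Definition.** A reader might infer that the SAP defines a response assessment, for censoring, as including NE. It does not. The NE parenthesis belongs to the Efficacy Population, and nothing in VII.A.3 carries it over. The supportable statement is that the term is undefined there and NE is not excluded.

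**Missed scans.** A reader might infer from Appendix 1 that a visit with no scan extends PFS or DOR. That is not shown. Appendix 1 assigns a status to a time point, not a date. Under SAP V.F a scan not done has no date and none is imputed, and "the progression date is derived from the date of the tumor scan that was used to determine progression". The natural fallback is the last scan performed. What stays open is an NE or response entry dated at a visit without imaging, such as an end-of-treatment visit under the 8-week exception.

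**Information in an NE scan.** An NE scan is not the same as no scan. In Table 21 of the protocol, overall NE requires no nontarget progression and no new lesion, since either would make the response PD. A scan that was done but rated NE is partial evidence against progression.

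**Size.** The simulation inputs are assumed, and a day-126 PFS estimate is not among the planned summaries. In a cohort of 3 to 14, one patient is 1/14 = 7% to 1/3 = 33%, more than any shift in the table.

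**Safeguards.** Death is a PFS event, discontinuation for progression is an event for DOR and TTP, and responses are listed by patient, so trailing NEs remain visible.

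None of this supplies the missing restriction to evaluable assessments.

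**Conclusion.** The point holds as a minor correction. As written, the rules let a dated trailing NE extend PFS or DOR by one 42-day interval each. They let a patient whose only assessment is NE contribute about 42 progression-free days, and they let TTP in completers run to a visit without imaging.

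The PFS and DOR effect is upward relative to censoring at the last evaluable scan. Its size depends on how often the last dated assessment is NE, which the documents do not say. The 0.4 to 3.9 points hold only under the assumptions listed, including that NE is unrelated to progression and always dated. The median will often not change, but a quartile in a small cohort can.

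A reader might infer that the trial's conclusions are at risk. The documents do not support that: these endpoints are exploratory (SAP II), the efficacy analyses are descriptive (SAP VII), and dose decisions rest on Cycle 1 DLTs (Protocol 4.2.3).

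**What to change.** In SAP VII.A.3, replace the separate censoring phrases with one rule for PFS, TTP and DOR: patients without an event are censored at the date of their last evaluable tumor assessment, meaning an overall response other than NE. For PFS and TTP, censor at Day 1 if there is no evaluable post-baseline assessment and no event. DOR needs no such fallback, because the response itself is an evaluable assessment. Apply the rule to TTP completers in place of the last-visit date.

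State also that the date used is the scan date, which settles response entries recorded at visits without imaging.

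The cost is a sentence or two before the SAP is finalized, with no new data collection. The estimates may come out slightly shorter.
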